Acceptability and Feasibility. Pilot work with HOPE clearly demonstrates the feasibility of engaging residents of battered women's shelters in HOPE. Our data show that our population has chronic PTSD symptoms that have persisted an average of nearly 38 months. Our initial randomized trial of the shelter version of HOPE³⁷ had low treatment drop-out rates (5.7%), high credibility ratings (average of 6.78 on 8 point scale), and satisfaction with treatment was also high (e.g., averages of 3.4 – 3.5 on 4 point satisfaction ratings). Further, consistent with research that finds that 38% of IPV victims fail to initiate treatment⁷ and with the literature that describes the barriers to accessing mental health treatment in IPV victims⁶, our data support that simply offering referrals to community based treatment is not successful, with 60% of control participants failing to follow-up with referrals for community-based treatment while in shelter. Given that 83% of our sample either reported further IPV, contact with their abuser, and/ or another significant trauma after leaving shelter, we expanded HOPE to also include sessions after women leave shelter (i.e., 16 sessions starting in shelter and extending until 3-months post-shelter). Results of a recently completed randomized clinical trial of this expanded version of HOPE support the acceptability and feasibility of continuing treatment after shelter. Of the 30 participants who were randomized to the expanded HOPE, 25 (83%) completed 10 or more sessions of HOPE, with women completing an average of 80% of available post-shelter sessions ($M=12.7$ sessions). *Thus, results clearly support our ability to maintain our engagement with women in HOPE after leaving shelter.* This study also had low treatment drop-out rates (6.7%), high credibility ratings ($M = 6.94$ on 8-point scale) and high treatment satisfaction ($M = 3.8$ on 4-point scale). *Thus, our work to date suggests that the strategies included in the expanded version of HOPE have been successful in addressing many of the clinical and research challenges faced by victims of IPV who seek shelter.*

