Initial Efficacy of HOPE. Our pilot work with both the shelter and expanded version of HOPE also provides initial support of the efficacy of HOPE. In a randomized trial of the shelter version of HOPE³⁷, we found HOPE to be associated with significant treatment gains, most importantly, reduced PTSD arousal ($d = 1.05$) and avoidance symptoms ($d = .52$) and lower likelihood of experiencing further abuse by a current or former partner. Further, women who completed a minimal number of sessions of HOPE were over 2 times less likely to meet criteria for PTSD or subthreshold PTSD after leaving shelter (OR's range from 2.33 to 4.44 from 1-week to 6-months post-shelter). Additionally, women who completed at least 5 sessions of HOPE were over 12 times less likely to report being abused over the course of a 6-month follow-up (OR = 12.6) relative to participants who did not receive HOPE. Participants who received HOPE also reported less severe depression and greater degree of social support and empowerment across the 6-month follow-up than did women who only completed standard shelter care. Finally, data suggest that HOPE may have an impact on children, where participants in the control group experienced an increase in parenting stress from 1-week post-shelter to 3-months post-shelter, while participants' in the treatment group level of parenting stress remained stable. This finding suggests that HOPE may provide skills that generalize to parenting in IPV victims. Results of a recently completed randomized trial of the expanded version of HOPE that will be used in the proposed study found significant treatment effects for PTSD (*Cohen's d* = .67), social adjustment (*Cohen's d* = .44) and social support satisfaction (*Cohen's d* = .89) and trends for depression severity (*Cohen's d* = .45), revictimization severity (*Cohen's d* = .51), and empowerment (*Cohen's d* = .5). Minimal attendance analyses find significant treatment effects for depression severity (*Cohen's d* = .65), social adjustment (*Cohen's d* = .63), empowerment (*Cohen's d* = .72), and trends for PTSD (*Cohen's d* = .72), revictimization severity (*Cohen's d* = .55), social support satisfaction (*Cohen's d* = .95). Overall, women who participated in HOPE exhibited less severe PTSD symptoms, less revictimization, fewer depression symptoms, and less impaired functioning, as well as a greater degree of empowerment, and greater satisfaction with social support relative to those who did not complete HOPE. Chi-square analyses also revealed that significantly fewer HOPE participants met criteria for IPV-related PTSD at post-treatment and were unemployed 6-months after leaving shelter relative to controls. *Therefore, results of our randomized pilot study of this expanded version of HOPE provide evidence of the feasibility and initial efficacy of on participants' PTSD symptoms and abuse severity.*

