Rationale for the study design: Pilot work with HOPE has determined that HOPE is associated with improved outcomes relative to standard shelter services alone. Given that there is no other existing PTSD treatment appropriate for this population that could serve as a comparison condition the next logical stage in evaluating the efficacy of HOPE is to determine if HOPE offers improvement over a credible control condition that controls for the nonspecific components of therapy. PCT (see appendix) is a problem-focused, supportive therapy that is frequently used as an attention-matched control condition in clinical trials of PTSD^{46, 47}. PCT does not incorporate any of the hypothesized active ingredients of HOPE (e.g., cognitive-restructuring, acquisition of new behavioral skills, safety planning, access to resources, and empowerment strategies), but does provide psychoeducation on PTSD. Further, PCT is also clinically realistic, as many practitioners incorporate this approach into their standard practice⁴⁸. Therefore, we chose to compare HOPE to PCT, in order to determine if components specific to HOPE are responsible for observed effects, rather than nonspecific factors consistent with supportive therapy. [name] who has established expertise in PCT⁴⁶ will assist in adapting PCT to meet the needs of the proposed study, as well as in the training and supervision procedures for the PCT arm of this study.

Sample and recruitment: Participants will be 186 women recruited over 27 months from six battered women's shelters in five different counties within a 55 mile radius of the University of Akron (see letters of support) and randomized either to receive HOPE ($n = 93$) or PCT ($n = 93$). Both treatments will start while women are residents of shelter and extend after they leave shelter. Given that the length of shelter stay is variable and outside of experimenter control, session frequency will be individualized based on length of shelter stay. We are currently employing this model in our work with HOPE with success (see C1). Participants in both treatment conditions will receive up to ten individual sessions while in shelter, and 16 sessions in for up

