Adequacy of Sample Size: Optimal Design 2.0 Software⁵³ was used to conduct power analyses for hierarchical linear modeling (see C3) of treatment effects. An alpha level of .05 was chosen for each of the primary hypotheses. Given that our pilot research has found medium effect size (ES) on the higher end of the continuum for PTSD severity and medium ES for re-abuse severity (see C1), a more conservative medium ES (delta = .60; which is on the lower end of the continuum of medium effect sizes) was assumed in an effort to account for the potential for reduced effects in the current study. We also assumed an ES variability of .07 across the 6 shelters where recruitment will occur. An ES variance of .07 corresponds to a standard deviation of approximately .2, which for ES = .60 reflects substantial variation in treatment ES across shelters. Thus, we are powering the study to be able to detect a medium ES, even if there is substantial ES variability across shelters. Additional assumptions for the power analysis included a proportion of explained variance by the blocking variable (i.e., shelter) of .1 and a proportion of explained variance by the level 1 covariate (i.e., baseline PTSD or violence severity), of .3. There is little literature on which to base estimates of these two parameters for the proposed study, but these parameters have relatively little effect on sample size requirements given the specified ES, ES variability, and number of shelters. For example, the most extreme value of 0 (instead of .1) for the proportion of explained variance by the blocking variable would only increase the necessary sample size by 2 per shelter. Also, even an extreme value of .1 (instead of .3) for proportion of explained variance by the baseline level of the outcome variable would only increase the necessary sample size by 5 per shelter. Using the parameter estimates specified above and a desired power of .80, results of the

power analysis indicated that 25 participants were required per shelter for a total N of 150. In our pilot research we had retention rates of 81-95% (see C1). Thus, assuming the more conservative attrition rate of approximately 20%, we would need 31 participants per shelter, for a total of 186 participants to achieve a power of .80 to detect medium-sized treatment effects for our primary outcomes.

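### The planning effect of .60 is described as conservative, but for re-abuse severity it is larger than the pilot effects of .51 and .55, at which power is about .68 and .74

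*Combined protocol and SAP*

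**What the plan says.** C2, Adequacy of Sample Size, gives the pilot results for PTSD severity (described as at the upper end of medium) and re-abuse severity (described as medium) as the basis for the planning effect. It then says that "a more conservative medium ES (delta = .60; which is on the lower end of the continuum of medium effect sizes) was assumed", and gives the purpose: "in an effort to account for the potential for reduced effects in the current study". The paragraph ends with 25 women per shelter in six shelters (150 analysed), raised to 31 per shelter for attrition, "for a total of 186 participants to achieve a power of .80 to detect medium-sized treatment effects for our primary outcomes".

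The pilot figures are in C1, Initial Efficacy of HOPE. The trial of the expanded version, which is the version to be tested here, "found significant treatment effects for PTSD (*Cohen's d* = .67"). The same paragraph lists, as a trend, "revictimization severity (*Cohen's d* = .51") and, in the minimal attendance analysis and again as a trend, "revictimization severity (*Cohen's d* = .55"). The minimal attendance value for PTSD is .72.

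The Assessment part of C2 names PTSD severity and degree of re-abuse as the primary outcomes and scores re-abuse as severity. The rationale for the study design says that the next step is to "determine if HOPE offers improvement over a credible control condition that controls for the nonspecific components of therapy".

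**The concern.** A planning effect is conservative relative to a pilot only if it is smaller than the pilot effect. The paragraph makes that claim for a single value drawn from two outcomes, and it is true of only one of them. For re-abuse severity, .60 is larger than both reported pilot values.

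The change of comparator makes this matter more. The pilot compared HOPE with standard shelter services; this trial compares it with a therapy chosen to match nonspecific effects. That is a reason to expect smaller effects, and the paragraph says it has allowed for this. For re-abuse it has not.

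A reader who takes the power statement at face value will believe that both primary outcomes have .80 power with a margin below the pilot. A non-significant re-abuse result could then be taken as stronger evidence against an effect than the design supports.

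**Working it through.** **Inputs** (C2, Adequacy of Sample Size, unless noted)

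- Shelters J = 6; analysed per shelter n = 25
- Effect-size variance across shelters s² = .07
- Variance explained by shelter B = .1; by the baseline covariate R² = .3
- Alpha .05 for each primary hypothesis. Sidedness is not stated. Two-sided is assumed, because a one-sided test would need only 14 per shelter and does not reproduce the plan.
- Pilot effects (C1): PTSD .67; re-abuse severity .51 and .55

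**Formula.** For a multisite randomized trial with 1:1 allocation and a treatment effect that varies randomly across shelters:

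λ = J·d² / [s² + 4(1 − R²)(1 − B)/n]

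The test is F on 1 and J − 1 = 5 degrees of freedom, and power comes from the noncentral F with noncentrality λ.

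**Reproducing the plan.** The denominator is .07 + 4 × .7 × .9 / 25 = .07 + .1008 = .1708. At d = .60, λ = 6 × .36 / .1708 = 12.65 and power is .809. The smallest n that reaches .80 is 25, as stated. With B = 0 the requirement is 27, which matches the plan's increase of 2. With R² = .1 it is 31, an increase of 6 where the plan says 5.

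**Comparing .60 with the pilot**

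- PTSD: .60/.67 = .896, about 10% below
- Re-abuse: .60/.51 = 1.18, 18% above
- Re-abuse, minimal attendance: .60/.55 = 1.09, 9% above

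**Power at 25 analysed per shelter**

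| d | λ | Power |
|---|---|---|
| .67 (pilot PTSD) | 15.77 | .883 |
| .60 (plan) | 12.65 | .809 |
| .55 (pilot re-abuse, minimal attendance) | 10.63 | .741 |
| .51 (pilot re-abuse) | 9.14 | .679 |

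The effect detectable with power .80 is .593.

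**Sensitivity, one input changed at a time**

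| Change | Power at .51 | Power at .55 |
|---|---|---|
| B = 0 | .652 | .715 |
| Residual variance taken as 1 − R² − B | .690 | .753 |
| All 31 per shelter fully informative | .729 | .789 |
| s² = .04 | .758 | .816 |

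At .51 no single change reaches .80; s² = .04 together with 31 per shelter gives .815. At .55, s² = .04 alone is enough. The variance of .04 comes from the plan's remark that its .07 corresponds to a standard deviation of about .2, whereas √.07 = .265. With .04 the plan would have needed only 19 per shelter at d = .60, so .07 is the value behind its 25.

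**Illustration of a reduced effect.** If re-abuse received the same proportional reduction that .60 represents for PTSD, .51 × .896 = .457 gives power .586, and .55 × .896 = .493 gives .649. The plan states no such rule; this only shows the direction and rough size.

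**Precision of the pilot.** C1 refers to "Of the 30 participants who were randomized to the expanded HOPE". The number of controls is not given; assume 30. Then SE(d) ≈ √(2/30 + .51²/120) = .262, and the 95% interval around .51 runs from about 0.00 to 1.02.

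**The case against.** The strongest reply is that no stated number is wrong. The plan claims .80 power for medium-sized effects, and at .60 it has that. The word conservative might be read as a step down from the PTSD effect alone, since that is the one placed at the upper end of medium. But the sentence names both outcomes as its basis, and its conclusion covers both primaries. Even on the narrower reading, the paragraph never says that the re-abuse pilot lies below .60. It also calls that pilot effect medium, so promising .80 for medium effects does not rescue the claim at .51.

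Second, the power figures depend on the model. They treat the shelter-by-treatment effect as random, tested on 5 degrees of freedom at a single endpoint. The analysis section describes hierarchical models of trajectories and names no such random term. With shelter as a fixed block and the same explained variances, power at .51 with 150 analysed would be about .97. Repeated measures would also change the figures, and the documents give no correlations with which to work that out. This limitation stands. However, the fixed-block model is not the one used to size the trial, and the ordering of .51, .55 and .60 does not depend on any model. Nor is the shortfall at .55 robust to the variance: s² = .04 removes it.

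Third, the pilot is weak evidence: the gap of .09 is about a third of the approximate standard error. That is true, and .51 should not be treated as the truth. But the plan itself cites the pilot as its basis, and imprecision does not place .60 below .51.

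Finally, the earlier shelter-version trial reported an odds ratio of 12.6 for re-abuse. It concerns occurrence of abuse in women who completed at least five sessions, not severity, so it does not support .60.

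**Conclusion.** The concern holds. The description of .60 as conservative is wrong as written for re-abuse severity, one of the two primary outcomes, and correct for PTSD severity. Under the model that reproduces the plan's 25 per shelter, power for re-abuse is about .68 at the pilot value of .51 and .74 at .55, against the .80 claimed at .60. Changing one input at a time moves the figure at .51 between .65 and .76. These values assume a two-sided test, 150 analysed women, an effect-size variance of .07 and a single endpoint. They describe the power at the plan's own pilot values and do not predict the true effect. The sample-size calculation at .60 is not in dispute. The statement should be corrected, but the design does not fail because of it.

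**What to change.** Keep N = 186 and replace the justification in C2, Adequacy of Sample Size, with wording such as:

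> With 186 women enrolled and 150 analysed, power is .80 for an effect of about .59 to .60. This is below the pilot effect for PTSD severity (.67) but above the pilot effects for re-abuse severity (.51; .55 in the minimal attendance analysis). Under the same model, power for re-abuse severity is about .68 at .51 and .74 at .55, and lower if the attention-matched control reduces the effect. The pilot estimates are imprecise.

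Drop the claim that .60 is conservative for re-abuse. Add that a non-significant re-abuse result will be interpreted from its confidence interval. State the model behind the power figures (random treatment effect across shelters, single endpoint, variance .07), so that readers can see what they depend on.

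The cost is a less favourable power figure for one primary outcome. No extra participants are needed, and outcomes, analysis and conduct do not change. For scale, .80 power under this model would need 45 analysed per shelter (270 in total) at .51, or 33 (198) at .55; the fix does not ask for this.

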Randomization: In order to ensure that the treatment conditions are balanced on variables that might influence outcome (i.e., use of psychotropic medications and substance use), participants in each subgroup will be assigned to their treatment condition using an urn randomization procedure⁵⁴. Urn randomization is a stratified randomization technique that randomly assigns participants in a given subgroup to treatment conditions, but systematically biases the randomization in favor of balance among treatment conditions. We will stratify participants according to comorbid substance use disorder (SUD) and use of psychotropic medications to obtain an equal distribution of participants using medications or with SUD in each condition.

Potential for Cross-Contamination: The shelter is a close community and participants in HOPE may share HOPE specific components with participants in PCT. We considered randomizing treatment assignment to shelter rather than participants in an effort to eliminate the potential for cross-contamination. However, this strategy significantly reduced our power and required a sample size that was not feasible or cost effective. Further, in our pilot work with HOPE only 2 participants in the control group reported that participants in HOPE shared HOPE-specific information with them, with exploratory analyses revealing no differences in PTSD outcomes between those who reported exposure and those who did not. Further, HOPE focuses on empowerment and provides individualized feedback and customized handouts, thus the content of HOPE cannot be easily learned through exposure to a handout or a brief conversation. However, to minimize the likelihood of cross-contamination between treatment and control groups, we will (1) instruct participants to not share their materials (i.e., workbook) with other shelter residents, (2) assess whether participants randomized to HOPE shared HOPE specific information with other shelter residents, and whether participants randomized to PCT were exposed to specific HOPE components during our follow-up procedures, and (3) assess use of HOPE specific skills in the PCT group in order to determine if women in PCT were actually implementing skills taught only in HOPE. Thus, we will try to minimize the potential for sharing HOPE-specific information and skills between participants, but also assess whether cross-contamination is a significant problem (see C3).

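### The trial is powered as a design blocked on shelter, but shelter is neither a randomization factor nor a stated term in the primary model

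*Combined protocol and SAP*

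**What the plan says.** **Power (C2, Adequacy of Sample Size).** "Optimal Design 2.0 Software⁵³ was used to conduct power analyses for hierarchical linear modeling (see C3) of treatment effects". The inputs are "a more conservative medium ES (delta = .60"), an effect variance of .07 ("We also assumed an ES variability of .07 across the 6 shelters where recruitment will occur"), "a proportion of explained variance by the blocking variable (i.e., shelter) of .1", and a baseline covariate explaining .3. The result is stated per shelter: 25 evaluable, raised to 31 for attrition, giving totals of 150 and 186.

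**Setting (C2, Sample and recruitment).** Recruitment is from "six battered women's shelters in five different counties within a 55 mile radius". The only allocation figure is 93 per arm overall.

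**Allocation (C2, Randomization).** Participants, not shelters, are randomized by an urn whose stated purpose is to balance variables that could affect outcome. Two are named: "We will stratify participants according to comorbid substance use disorder (SUD) and use of psychotropic medications to obtain an equal distribution". Nothing says that the urn is run separately in each shelter.

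**Analysis (C3).** The HLM compares trajectories between the two groups. Length of shelter stay is offered as an example of a possible covariate; shelter itself is not mentioned. Covariates are to be added if the groups are found to differ.

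**The concern.** A multi-site calculation that counts shelter as a block compares HOPE with PCT inside each shelter, in near-equal numbers, and removes shelter differences from the error. Two later steps must deliver this: allocation has to keep the arms close to even within shelters, and the model has to contain shelter. The plan secures the first only by chance and does not commit to the second.

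Shelter also meets the plan's own criterion for an urn variable. Apart from the baseline value of the outcome, it is the only factor to which the sample size section assigns a share of outcome variance. At stake are a small loss of precision, a larger one if shelter is also missing from the model, and a choice of covariates that depends on the data.

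**Working it through.** **1. Reproduce the plan's figure.** Inputs from C2: J = 6 shelters, δ = .60, effect variance τ = .07, shelter share B = .1, covariate share R² = .3, "An alpha level of .05 was chosen for each of the primary hypotheses" (taken as two-sided, since one-sided would give 14 per shelter), and power .80. For a person-randomized trial with random site effects and a 1:1 split in every shelter:

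- Variance of one shelter's effect: v = τ + 4(1−B)(1−R²)/n
- Noncentrality: λ = Jδ²/v, tested on F(1, J−1) = F(1, 5)

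With (1−.1)(1−.3) = .63 and n = 25:

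- v = .07 + 4(.63)/25 = .07 + .1008 = .1708
- λ = 6(.36)/.1708 = 12.65, power **.809**
- n = 24 gives .7999, so 25 is the smallest n that reaches .80, as stated.
- B = 0 requires 27, the plan's extra 2 per shelter. R² = .1 requires 31, an extra 6 against the plan's 5.

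The stated 25 therefore belongs to a design balanced within shelters, with shelter taken out of the error.

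**2. Shelter left out of the urn.** Simulating 6 × 25 women with shelter variance .10 and residual .63, and setting τ aside for the moment, the SE of the treatment effect is .1296 (balanced within shelter, shelter adjusted), .1318 (not balanced, adjusted) and .1373 (neither). Restoring τ adds .07/6 = .01167 to each squared SE. F(1, 5) is kept throughout.

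| Shelter in urn | Shelter in model | SE | Increase | λ = .36/SE² | Power |
|---|---|---|---|---|---|
| balanced | yes | √(.01680 + .01167) = .1687 | – | 12.65 | .809 |
| no | yes | √(.01737 + .01167) = .1704 | 1.0% | 12.40 | .802 |
| no | no | √(.01885 + .01167) = .1747 | 3.5% | 11.80 | .783 |

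Two checks agree:

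- Losing B in the formula gives v = .07 + 4(.70)/25 = .182, λ = 11.87 and power .785.
- A simulation of the urn itself, with shelter in the model, gives mean power .802 (5th percentile .794) without shelter as a factor and .806 with it. It assumes SUD in 25%, medication use in 35%, a UD(1,1) urn and equal shelter sizes; none of these is in the documents.

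**3. How uneven shelters can become.** For coin-toss allocation of 31 women, X ~ Binomial(31, .5). The chance for at least one of six shelters is 1 − (1 − p)⁶. The inflation of a shelter's sampling variance for an a:b split is (1/a + 1/b)/(4/31).

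| Split or worse | p per shelter | At least one of six | Inflation at that split |
|---|---|---|---|
| 11:20 | .150 | .62 | 1.092 (9%) |
| 10:21 | .071 | .36 | 1.144 (14%) |

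These inflations apply to sampling variance only. With τ included, 10:21 raises the shelter's variance from .07 + .63(4/31) = .1513 to .07 + .63(1/10 + 1/21) = .1630, about 8%. The coin toss slightly overstates imbalance. In the urn simulation, 5.7% of shelters and 29% of trials had a HOPE share outside 1/3 to 2/3. With shelter as a factor these fell to 0.4% and 3%.

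**The case against.** The strongest reply is that this hardly matters. With shelter in the model, leaving it out of the urn costs under one point of power (.809 to .802), and adding it buys back about 0.4 points on average (.802 to .806). Two patient-level factors are a defensible choice, the plan itself says that the shelter parameter has little influence on sample size, and C3 will check the randomization and adjust if groups differ.

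Most of this stands. The urn omission alone is minor, and the greater part of the recoverable loss comes from the analysis. The C3 safeguard is only partial: it is triggered by observed differences, does not name shelter, and could miss shelter variation that matters for precision even when the arms look balanced.

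Four stronger readings are tempting, and the documents do not support them:

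- **The trial is underpowered or 186 is wrong.** Power stays at about .80 if shelter is in the model.
- **The comparison is biased.** Individual randomization is intact; any shelter imbalance is due to chance.
- **The extra 2 per shelter is the plan's own price for not stratifying.** That figure is for shelter explaining 0 instead of .1 of the variance. It concerns prognostic strength, not allocation.
- **The SE rises by 5–6%.** That follows (.1373/.1296 = 1.059) only if the .07 effect variance is dropped. With it, the rise is 3.5% at most.

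Nor is there a planned shelter-specific effect to protect: shelter is not among the moderators listed in C3.

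**Conclusion.** The mismatch is real and its consequence is modest. Power is about .81 for the blocked design, about .80 if shelter is only in the model, and about .78, just under target, if it is in neither. Markedly uneven shelters are likely: the chance of 11:20 or worse in at least one of six is about .62 under coin-toss allocation. Their effect on the overall comparison is small.

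A reader might infer from C3's silence that shelter will be left out of the model. The documents do not say so; the power statement refers to the C3 model and calls shelter a block. What can be said is that C3 does not commit to it.

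The figures rest on the plan's inputs, a two-sided test, equal shelter sizes and F(1, 5) in every scenario. Unequal shelters would be more uneven: with assumed recruitment shares of 30/25/20/12/8/5%, about 46% of simulated trials had a shelter with a HOPE share outside 1/3 to 2/3.

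**What to change.** 1. **C2, Randomization:** add shelter (six levels) as a third urn variable beside SUD and psychotropic medication use. If the urn balances on margins, a full cross-classification (6 × 2 × 2 = 24 cells) is not needed.
2. **C3, Primary and Secondary Outcomes:** specify shelter as a block or level in the primary HLM regardless of observed imbalance, and say whether the treatment effect is allowed to vary by shelter, as the power calculation assumed.

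The sample size does not change. The cost is one more field in the randomization program, slightly weaker balance on SUD and medication use, and a few degrees of freedom for shelter. The first change cannot be applied to women already allocated. The second can be made at any time before unblinded data are examined and recovers most of the loss, so it should be made in any case.
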